#### 7.3.2 Patient EHR data for Exclusion criteria for Aims 1 and 2:

- (1) Age <18 years of age or >99 years of age at index event;
- (2) Pre-existing ASCVD prior to index event, including a previous diagnosis of any acute myocardial infarction, heart failure, acute coronary syndromes, stable or unstable angina, arterial

revascularization (includes coronary arterial or peripheral), stroke, transient ischemic attack or peripheral arterial disease presumed to be of atherosclerotic origin determined by ICD codes;

- (3) Encounter with cardiology specialist within 1 year prior to index
- (4) Evidence of ART for pre-exposure prophylaxis (i.e., Truvada [emtricitabine/tenofovir disoproxil fumarate] or post-exposure prophylaxis (e.g., Truvada plus raltegravir) without HIV diagnosis.

## 7.4 Inclusion and exclusion criteria for Aim 3

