## 7.2 Study sites

#### 7.2.1 Study Sites for Aims 1 and 2

Aims 1 and 2: Coordinating Center will collect health system data from Duke University Health System and Vanderbilt University Medical Center, and Medical University of South Carolina, and Wake Forest University Health Sciences via the STAR CRN using CDM.

#### 7.2.2 Study Sites for Aim 3

Aim 3: Duke University Health System, Vanderbilt University Medical Center, Medical University of South Carolina will identify patients and health care providers for interviews; Case Western Reserve University will identify only health care providers for interviews.

Participants will be identified/consented for the qualitative interviews from the following sites:

Duke University Health System (DUHS): Patients & Health Care Providers
 Vanderbilt University Medical Center (VUMC): Patients & Health Care Providers
 Medical University of South Carolina (MUSC): Patients & Health Care Providers

Case Western Reserve University (CWRU): Health Care Providers

## 7.3 Inclusion and exclusion for Aims 1, 2 and 3

#### 7.3.1 Patient EHR data for Inclusion criteria for Aims 1 and 2

- (1) Race equals Black/African-American, American Indian/Alaska Native, Asian, Native Hawaiian/Pacific Islander, or More than one race, and/or Ethnicity equals Hispanic or Latino;
- (2) Documented evidence of HIV positive status (HIV positive diagnosis (ICD10 codes B20-B24, or ICD9 codes 042, V08) and prescription of antiretroviral therapy (ART));
- (3) Documented evidence of elevated AtheroSclerotic CardioVascular Disease risk (ACC/AHA ASCVD 10 year risk ≥5%²⁴, or Framingham Cardiovascular Disease 10 year risk ≥5%²⁵) after HIV diagnosis. The date when the patient first meets either of these CVD risk thresholds and with 1 prior encounter not having CVD risk score defines the **index** time-point for Aim 1 of this study. These risk calculations depend on sex, age, body mass index, diabetes, current smoking, total cholesterol, HDL cholesterol, systolic blood pressure, and treatment for hypertension (defined from diagnosis codes). If cholesterol measures are not available, then body mass index may be used in place of lipids in the Framingham risk calculation; **NOTE: must have at least one prior encounter within 365 days within health system prior to index**
- (4) Presence of a modifiable risk factor: hypertension, diabetes, elevated total cholesterol, elevated LDL cholesterol and/or tobacco use.

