## 8 Study Procedures

## 8.1 Aims 1 and 2 Study Procedures

We will analyze patient-level and provider-level data from electronic health records (EHRs) from STAR Clinical Research Network (CRN) institutions using CDM. These institutions include Duke University Health System, Vanderbilt Universities, and Medical University of South Carolina.

We (DCRI CC) will retrospectively ask the DataMarts to query the EHR for eligible patients based on age, race, ethnicity, and HIV diagnosis to identify Black/African-American and other URM PLWH. Additional data that are already collected as part of routine medical care will be extracted by sites

from patient EHRs starting at the first clinical contact after January 1, 2010, to create a contemporary cohort with at least 5 years of longitudinal follow-up data. Longitudinal follow- up data will be collected through December 31, 2020. Data will be reviewed and or collected from patient EHR from January 1, 2010 through December 31, 2020. Patients will be included for analysis in this retrospective study at the time of the first clinical encounter during an ("eligibility period") when they meet the inclusion/exclusion criteria (listed below), with a "look back period" of 1 years prior to "enrollment" (i.e., back as far as 2010) to establish medical history and other baseline factors. These dates may be adjusted during the course of the study depending on availability of data in the various DataMarts. The overall scientific premise is depicted in Section 8.2 which shows our approach without specific dates.

DataMarts, Site PIs and Site study teams will link local EHR records with death events and cause of death prior to sending the final dataset to the DCRI CC. Sites will query and link records using National Death Index Plus, State Death records, Social Security Death Mastefile, Hospital death record and/or similar death record for causes of death including cardiovascular death, retaining protected health information needed to query these databases at the site level.

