## 12 Data analysis & statistical considerations

#### 12.1 Analysis Plan for Aim 1

For this aim, the primary outcome variable is referral to a cardiology specialist within 6 months of baseline. This will be measured as a binary variable, with 'yes' defined if there is documented evidence that a referral is made within 6 months of becoming eligible by CVD risk score and kept within 3 months of referral, and 'no' otherwise. We will also determine the time from baseline to cardiology referral and the time until the first visit with the cardiology specialist.

We will consider a number of patient and provider factors evaluated at baseline that are potentially associated with referral to a cardiology specialist. Patient factors will include demographic factors (age, sex, race, ethnicity), level of ASCVD risk, Charlson comorbidity index, SES (e.g.; 5 digit zip code, health insurance ([yes/no]), type of health insurance (Medicare, Medicaid, private, Ryan White, etc.), and history of keeping appointments during 2 years prior to baseline. Provider factors will include primary management strategy (coprimary management defined as having both an HIV doctor and Primary Care Practitioner vs. HIV provider as primary care), and years of practice since training. Cardiologist availability will be a site-determined variable. Based on prior literature, we are specifically considering sex as a biological variable that may be related to specialty referral. 

Baseline characteristics of the cohort will be summarized overall and by referral status. We will include the patient and provider factors described above, as well as vital signs (including weight, body mass index and blood pressure), laboratory measures (particularly total and HDL cholesterol, CD4 cell count, HIV viral load), and relevant medications (ART and cardiovascular medications). We will document the patterns of HIV related CVD comorbidity in the study population, as the funding opportunity announcement specified.

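### A first ASCVD event coded on the index date or later in the same encounter is not excluded, so post-event follow-up can count as preventive cardiology referral

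*Combined protocol and SAP*

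**What the plan says.** Section 7.3.1(3) defines index as "The date when the patient first meets either of these CVD risk thresholds", subject to one earlier encounter without a risk score and the note that the patient "must have at least one prior encounter within 365 days within health system prior to index". Neither condition names a type of encounter. If lipids are missing, "then body mass index may be used in place of lipids in the Framingham risk calculation", so a blood pressure and a body mass index can complete a Framingham score.

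Section 8.1 adds: "Patients will be included for analysis in this retrospective study at the time of the first clinical encounter" at which the criteria are met. It does not limit that encounter to ambulatory care.

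Two exclusions in section 7.3.2 look backwards from index. Exclusion 2 covers "Pre-existing ASCVD prior to index event, including a previous diagnosis of any acute myocardial infarction" and a list of other ASCVD conditions. Exclusion 3 covers "Encounter with cardiology specialist within 1 year prior to index". Neither mentions the index date itself or the index encounter.

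Section 12.1 scores the Aim 1 outcome 'yes' on "documented evidence that a referral is made within 6 months of becoming eligible by CVD risk score", provided the appointment is kept within three months. Section 12.2 uses that same variable as the Aim 2 exposure and matches referred to non-referred patients on it.

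**The concern.** Aim 1 asks what leads to cardiology referral among patients at raised risk who do not yet have ASCVD. An admission for a first event is an occasion on which blood pressure and lipids are measured, so it can be the first encounter with a qualifying score. If the event is coded that day or later in the stay, it is not prior to index and exclusion 2 does not reach it. Nor does exclusion 3 reach cardiology care given during that stay.

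Two things follow.

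- **Aim 1:** follow-up prompted by an event is recorded as preventive referral. A candidate factor that tracks presentation in acute care, such as insurance type or appointment history, could pick up part of that signal.
- **Aim 2:** these patients concentrate in the referred group. The matching factors named in section 12.2 include age, sex, race/ethnicity, insurance, risk score, comorbidity index, site and year. An event at index is not named, so a post-event patient can be paired with an event-free control.

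**Working it through.** **1. Which patients the rules keep.** Index is a date. Take a multi-day admission for a first event:

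| Event code dated | Is it prior to index? | Result under exclusion 2 |
|---|---|---|
| Before the qualifying reading's date | Yes | Excluded |
| Same date | Not on the literal wording | Can be kept |
| Later in the same stay | No | Kept |

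Inclusion therefore turns on record dates within one admission. No other section settles the matter. The sensitivity analyses in section 12.1 vary follow-up intensity, the referral window and subgroups with extreme referral rates, but not care setting.

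**2. The plan's own power figures, for scale.** Inputs from section 12.2.1: 300 per group, control rates of 30% (BP) and 45% (lipids), increases of 10 and 15 points. The test is two-sided at 0.05 (section 12.2).

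Power = Φ{[d − 1.96√(2p̄(1−p̄)/n)] / √[(p₁q₁+p₂q₂)/n]}

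- BP: (0.10 − 1.96 × 0.03894)/0.03873 = 0.611, giving 72.9% (plan: above 70%).
- Lipids: (0.15 − 1.96 × 0.04077)/0.04031 = 1.739, giving 95.9% (plan: above 95%).

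Both figures reproduce and are not in dispute.

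**3. Share of 'yes' outcomes that would be post-event follow-up.** N = 1,350 is the midpoint of the plan's 1,200–1,500, and 22% lies within its 20–25% referral rate. The share s of index encounters that are first-event admissions and the 80% referral after an event are assumptions with no source in the documents.

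Share = 0.80sN / [0.80sN + 0.22(1−s)N]

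- s = 1%: 10.8/(10.8 + 294.0) = 3.5%
- s = 3%: 32.4/(32.4 + 288.1) = 10.1%

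Varying the assumptions (60–90% referred after an event, 20–25% otherwise):

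- s = 1%: from 0.006/(0.006 + 0.2475) = 2.4% to 0.009/(0.009 + 0.198) = 4.3%
- s = 3%: from 0.018/(0.018 + 0.2425) = 6.9% to 0.027/(0.027 + 0.194) = 12.2%

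A small share of the cohort becomes a share of the referred group roughly two to four times as large.

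**4. False odds ratio in Aim 1.** Take a binary factor with no true association, but with different shares a of first-event index dates at its two levels. The referral probability is p = 0.22(1−a) + 0.80a.

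- a = 4%: p = 0.2112 + 0.0320 = 0.2432, odds 0.3214
- a = 2%: p = 0.2156 + 0.0160 = 0.2316, odds 0.3014
- Ratio: 1.07

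At a = 8% against 2%, p = 0.2664, odds 0.3631, ratio 1.20.

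With the plan's 33% factor prevalence, the groups are about 445 and 905. For the 1.07 case the standard error is √[0.2354 × 0.7646 × (1/445 + 1/905)] = 0.0246, so the shift is 0.0116/0.0246 = 0.47 standard errors. The chance of p < 0.05 is Φ(−1.49) + Φ(−2.43) = 0.068 + 0.008, about 8% against the nominal 5%. The same calculation for the 1.20 case gives about 29%.

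**5. Cost of removal.** If 3.5% or 10% of 300 pairs were lost, about 290 or 270 would remain. BP power would be about 71% or 68.4%. The plan's own span of 250 to 375 per group moves it further, from 65.0% to 82.0%.

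**The case against.** The strongest reply is that the documents show only that these patients can enter. Several features limit the number:

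- Index is the first crossing of 5%, a prior encounter within a year is required, and body mass index can stand in for lipids. A patient already in care may well cross the threshold at a routine visit before any event.
- Section 8.1 ties entry to the encounter at which inclusion and exclusion criteria are met, which could be read as judging exclusions at that encounter.
- Section 12.2.1 expects MACE of about 5% at 5 years, roughly 1% a year. A 5% share at the index encounter alone would equal five years of expected events. This is a plausibility check rather than a bound, because exclusion 2 covers more conditions and events prompt measurement.
- The Aim 1 model adjusts for several of the factors concerned, and one planned sensitivity analysis drops subgroups in which referral is extremely common.

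This stands as far as size and certainty go. It does not close the gap: exclusion 2's own wording looks only before index, and the sensitivity analysis does not name first-event patients.

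A reader might also infer that any factor linked to acute care will emerge as a referral factor. The 1.07 result does not support that. Both false odds ratios lie well below the 1.5–1.6 for which section 12.1.1 gives power.

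A further tempting inference is that acutely raised blood pressures bring in patients with true risks of 3.5–4.5%. That range merges extremes. If risk rises as systolic BP to a power b, a usual reading of 130 raised by 10 mmHg with b = 1.5 inflates the score by (140/130)^1.5 = 1.12, so only true risks of at least 5/1.12 = 4.5% cross. A figure of 3.5% needs +20 mmHg and b = 2.5, a factor of 1.43. The documents give neither the exponents nor the size of any acute rise.

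**Conclusion.** The point holds as a gap in the cohort rule. A first ASCVD event coded on the index date, or later in the index encounter, is not excluded. Its cardiology follow-up then counts as a 'yes' in Aim 1 and as exposure in Aim 2. That is at odds with a primary-prevention cohort.

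The number affected is unknown. Under the stated assumptions, 1–3% of index encounters would produce about 3.5–10% of 'yes' outcomes, and the distortion of Aim 1 odds ratios would usually be small. The issue is cohort definition and the meaning of the outcome rather than power.

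Two stronger readings should be set aside. The index event would not be counted as an Aim 2 outcome, because section 12.2 starts ascertainment at the kept cardiology appointment. And the documents do not show that index must be restricted to ambulatory care in the primary analysis. That is a trade-off: it could drop or delay patients who rely on acute care, possibly including the uninsured, who belong to a subgroup of primary interest in section 12.1.

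**What to change.** In section 7.3.2(2), replace the prior-to-index limit with: on or before the index date, including diagnoses made during the index encounter. Report the number of patients this removes.

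Add to section 12.1, and carry into 12.2, a sensitivity analysis in which the index encounter and the systolic blood pressure and lipid values in the score come from ambulatory care only. Report how many patients are dropped or indexed later.

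The first change is a date and encounter condition in a query the coordinating center already has to write. The second is an encounter-type filter and one extra run. A few patients are likely to be lost. At the upper end of the illustration BP power would fall from 72.9% to about 68%, but the pairs lost are ones that do not belong in the comparison.

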#### Hypotheses to be tested:

- 1. We hypothesize that patient- (e.g., health insurance) and provider-level (e.g., patient-provider race discordance) factors are associated with cardiology referral in URM people living with HIV (PLWH) at elevated CVD risk. The primary outcome measure is visit with a cardiologist after meeting criteria for elevated CVD risk.
- 2. We hypothesize that URM PLWH who are seen by a cardiologist will have better CVD outcomes compared to those without referral. Primary outcomes are blood pressure and lipid control, and secondary outcomes are myocardial infarction, stroke, death and cardiovascular death both individually and as a composite, as a function of whether an individual at elevated CVD risk was seen by a cardiologist prior to first event.
  - a. We hypothesize that guideline-directed care including tobacco cessation counseling, cardiac testing, blood pressure and cholesterol medication management, glycemic control and appropriate use of statins mediate the relationship between cardiology referral and CVD outcomes.
- 3. Aim 3 is not driven by a pre-specified hypothesis.

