Starting with the population selected for Aim 1, we will create a sub-population by matching patients referred to a cardiology specialist (the primary outcome variable for Aim 1) to similar non-referred patients. The goal of this matching is to balance factors that may be confounders of the relationship between referral and cardiovascular outcomes. We will identify factors found to be associated with cardiology referral from Aim 1, as well as factors that are expected to be associated with outcomes such as, age, race, insurance status/type, ASCVD risk score, and comorbidity index. We will not seek to match on factors that may be associated with referral but unlikely to be directly associated with outcomes. For example, we may not want to match on cardiologist availability by site if this is only related to referral and not independently to outcomes. Variables that potentially modify the effect of referral (e.g., sex, race/ethnicity, insurance status) will be included among the matching factors. Patients will be matched within sites and year of baseline encounter.

For each patient referred to a cardiologist we will identify one non-referred patient (1:1 matching) within each site. We will match using values of the individual confounders, with an exact match on sex, race/ethnicity, insurance status/type, and to within a small caliper for continuous variables (e.g., ±5 years for age). Matched pairs will be identified using optimal matching. If this approach fails to identify an adequate number of matched pairs, then 1:1 matching will be implemented using a propensity score.

Once the matching has been implemented, the same baseline characteristics reported for Aim 1 will be summarized in the matched cohort by referral status. Metrics (e.g., standardized differences) will be reported to evaluate how well-balanced the referred and non-referred groups.

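### Exclusion 3 misses cardiology referrals open at index and older cardiology care, so some patients seen by a cardiologist after index are coded as not referred and can become unexposed Aim 2 controls

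*Combined protocol and SAP*

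**What the plan says.** Four parts of the combined protocol and SAP decide who is exposed.

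- **Section 7.3.2, exclusion 3** removes patients with an "Encounter with cardiology specialist within 1 year prior to index". It does not mention referrals placed but not yet completed, booked appointments, or cardiology care before that year.
- **Section 7.3.2, exclusion 2** removes "Pre-existing ASCVD prior to index event, including a previous diagnosis of any acute myocardial infarction, heart failure, acute coronary syndromes" and further listed conditions, with no time limit stated.
- **Section 12.1** codes the Aim 1 outcome as yes on the basis of "documented evidence that a referral is made within 6 months of becoming eligible by CVD risk score and kept within 3 months of referral". Every other case is coded no.
- **Section 12.2** builds the Aim 2 cohort by "matching patients referred to a cardiology specialist (the primary outcome variable for Aim 1) to similar non-referred patients". It adds: "For each patient referred to a cardiologist we will identify one non-referred patient (1:1 matching) within each site".

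The hypotheses in section 4 define the Aim 1 outcome differently: "The primary outcome measure is visit with a cardiologist after meeting criteria for elevated CVD risk". That definition needs no referral date. The Aim 2 hypothesis in the same section likewise turns on whether a cardiologist saw the patient before the first event.

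On available history, section 8.1 says: "Data will be reviewed and or collected from patient EHR from January 1, 2010 through December 31, 2020". Section 12.2.1 gives accrual as 2012 to 2016, and section 12.1 uses a two-year history of appointment keeping as a patient factor.

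**The concern.** The exclusion works on completed visits, while the outcome works on the date of the referral. A patient whose referral was placed shortly before index, perhaps in the same work-up that produced the risk score, passes the exclusion because no visit has yet taken place. The same patient then fails the yes rule because the referral came before eligibility. A former cardiology patient who returns after index without a new referral also slips through.

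In Aim 1, these patients count as not referred although a cardiologist saw them, which distorts the associations with patient and provider factors. In Aim 2, they can be drawn as unexposed controls. Section 12.2 sets time zero for a pair at the referred patient's kept visit, which can be up to 6 + 3 = 9 months after index. A control with a visit pending at index could therefore have seen a cardiologist before follow-up of the pair begins. If cardiology care improves blood pressure or lipid control, the contrast between the groups shrinks.

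**Working it through.** **1. How the rules classify each patient.** All rows assume no diagnosed ASCVD, since exclusion 2 removes the rest.

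| Patient | Exclusion 3 | Section 12.1 | Section 4 |
|---|---|---|---|
| Cardiology visit in the year before index | Removed | – | – |
| Referred before index, seen after index | Kept | No | Exposed |
| Last seen more than 1 year before index, returns without new referral | Kept | No | Exposed |
| Last seen more than 1 year before index, new referral made and kept in the window | Kept | Yes | Exposed |
| Last seen more than 1 year before index, never returns | Kept | No | Not exposed |

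The second and third rows are the problem. Section 12.1 does not say outright that the referral must follow index, but that is its natural reading, because the same paragraph also measures time from baseline to referral.

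**2. Whether another step catches them.** The matching factors named in section 12.2 do not include earlier or pending cardiology contact. The sensitivity analyses in section 12.1 restrict to patients in routine follow-up, lengthen the referral window forward to 12 months, or drop subgroups with extreme referral rates. None looks back before index.

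**3. The plan's own power figure.** Inputs from section 12.2.1: n = 300 per group; blood pressure control 30% against 40%; lipid control 45% against 60%. Section 12.2 gives two-sided alpha 0.05. The stated increases are read as absolute points, and the matching is ignored.

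Power = Φ{[(p1 − p0) − 1.96·√(2p̄(1 − p̄)/n)] / √([p0(1 − p0) + p1(1 − p1)]/n)}, where p̄ is the mean of p0 and p1.

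For blood pressure: (0.10 − 1.96 × 0.03894)/0.03873 = 0.611, so power is 73.0%. For lipids it is 95.9%. With a continuity correction the figures are 70.0% and 95.1%. The stated figures of more than 70% and more than 95% reproduce.

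**4. Assumed contamination.** Let f be the share of matched controls who carry the full effect. The control rate becomes 0.30 + 0.10f for blood pressure and 0.45 + 0.15f for lipids. The documents give no value for f.

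| f | BP difference (points) | BP power | Lipid power |
|---|---|---|---|
| 0% | 10.0 | 73.0% | 95.9% |
| 5% | 9.5 | 68.4% | 94.0% |
| 10% | 9.0 | 63.5% | 91.4% |
| 15% | 8.5 | 58.4% | 88.1% |

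Blood pressure power drops below 70% at f of about 3.3%, and lipid power below 95% at about 2.5%. If these controls carry only half the effect, 5% contamination gives 70.7% (BP) and 95.0% (lipid), and 10% gives 68.4% and 94.0%.

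**5. Room to exclude.** Section 12.1.1 expects 1,200 to 1,500 patients with 20% to 25% referred. That leaves 900 (1,200 × 0.75) to 1,200 (1,500 × 0.80) non-referred for 240 to 375 referred. Losing 5% to 20% of the non-referred leaves between 900 × 0.80/300 = 2.4 and 960 × 0.95/240 = 3.8 candidates per referred patient, before exact-match and caliper limits.

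**The case against.** A reader might infer that patients already in cardiology care generally end up as controls. The documents do not support that. Exclusion 3 removes anyone seen in the past year, and exclusion 2 removes those with diagnosed ASCVD. A former patient with a new referral kept in the window is coded yes, and one who never returns is arguably a correct no. Only patients picked by the 1:1 matching become controls.

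It can also be said that the mislabelling comes from the conflict between sections 4 and 12.1, not from exclusion 3 alone. That stands, and it is why reconciling the two is part of the fix. It does not remove the problem, because section 12.2 carries forward the Aim 1 outcome variable that section 12.1 defines by referral.

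A reader might also infer that two years of history can be checked for everyone, since records start in 2010 and accrual in 2012. Section 7.3.1 guarantees only one encounter in the 365 days before index, so this is not assured. The one-year rule also matches the general look-back in section 8.1, and a longer one is partly a matter of preference.

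Finally, a wider exclusion could remove referred patients too. Losing 5% of them (n = 285) gives 70.7% blood pressure power, and losing 10% (n = 270) gives 68.4%. This stands: the case for the change is a correct exposure label, and a gain in power is not assured.

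**Conclusion.** The point holds for two defined groups without diagnosed ASCVD: patients with a referral or appointment open at index who are seen afterwards, and former cardiology patients last seen more than a year earlier who return without a new referral. For them, section 12.1 gives a wrong exposure label, no other step in the plan corrects it, and section 4 would label the same patients as exposed.

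The size is unknown. The fall in blood pressure power from 73% to between 68% and 58% rests on an assumed 5% to 15% of matched controls carrying the full effect. With half the effect, 5% to 10% contamination gives 71% to 68%. Neither range is an estimate of what will happen. Nor can dilution be taken as certain: the bias is toward no difference only if the earlier or pending care is beneficial and these controls are otherwise comparable. The matter should be settled before the analytic query is run.

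**What to change.** 1. Reconcile section 4 with section 12.1, so that one definition of exposure (a visit after index, or a referral after index that is kept) governs both aims.
2. Add to exclusion 3: or a cardiology referral or appointment open at index.
3. Screen for earlier cardiology encounters over a fixed two-year window where the patient has that much history, and report how many do not. A fixed window avoids a look-back that grows longer for later entrants.
4. Report how many patients each part removes.
5. Keep the current one-year rule as a sensitivity analysis.

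The cost is mainly query wording. The plan already needs referral dates for the Aim 1 outcome, and section 8.1 already intends to capture specialist appointments missed after referral. The downside is somewhat fewer eligible patients, possibly including some referred ones, such as those referred in the very work-up that identified their risk. The counts in step 4 and the sensitivity analysis in step 5 will show how much this matters.

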Then, DCRI will take the query data that the sites provide to identify and further stratify data for potential cohort of patients, based on additional clinical characteristics. At the earliest clinical contact within look back period, we will identify HIV status according to ICD9/10 codes and prescription of ART. We will include individuals >18 years of age and < 99 years of age, plus will ascertain time-updated data for the following potential characteristics:

hemoglobin, creatinine (or glomerular filtration rate), age, sex, race, ethnicity, insurance status, total cholesterol, HDL cholesterol, LDL cholesterol, systolic blood pressure, prescription of anti-hypertensive medications, family history of coronary artery disease, presence of diabetes, previous diagnosis of any acute myocardial infarction, hospitalization for heart failure, acute coronary syndromes, stable or unstable angina, arterial revascularization, stroke, transient ischemic attack and peripheral arterial disease presumed to be of atherosclerotic origin determined by ICD9/10 codes. Behavioral factors are smoking status, number of clinic visits per year, length of time between clinic visits and missed appointments with specialist after referral. Data will also be ascertained on HIV viral load, CD4 count, prescription of any ART and length of time on all medications. This list captures the majority of the data related to our scientific aims and will be modified as the availability of these data are discovered.

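### Exclusion 4 duplicates inclusion 2 and so does not guard against a miscoded prophylaxis user; separately, 8.1 and 7.3.1 time the HIV case definition differently

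*Combined protocol and SAP*

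**What the plan says.** Several statements decide who counts as having HIV in Aims 1 and 2.

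- **7.3.1, inclusion 2** asks for "HIV positive diagnosis (ICD10 codes B20-B24, or ICD9 codes 042, V08) and prescription of antiretroviral therapy (ART". It gives no number of codes, no dates and no laboratory confirmation.
- **7.3.1, inclusion 3** requires elevated cardiovascular risk "after HIV diagnosis. The date when the patient first meets either of these CVD risk thresholds", and that date sets the index.
- **7.3.2, exclusion 4** removes people on ART for pre-exposure prophylaxis or "post-exposure prophylaxis (e.g., Truvada plus raltegravir) without HIV diagnosis".
- **8.1, site query:** sites are to "query the EHR for eligible patients based on age, race, ethnicity, and HIV diagnosis".
- **8.1, entry:** patients enter at the first encounter in the eligibility period "when they meet the inclusion/exclusion criteria (listed below", with one year of look-back "to establish medical history and other baseline factors".
- **8.1, HIV status:** "At the earliest clinical contact within look back period, we will identify HIV status according to ICD9/10 codes and prescription of ART".

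Section 8.1 also lists HIV viral load and CD4 count among the data to be collected. No eligibility rule uses either.

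**The concern.** There are two problems, with separate causes.

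The first is protection against prophylaxis users. Exclusion 4 shows that the sponsor saw them as a threat to the cohort. It acts only on people who lack an HIV diagnosis, and those people already fail inclusion 2. The person it would need to stop has a prophylaxis prescription and an HIV code entered in error. Exclusion 4 itself calls prophylaxis ART, so for that person the whole case definition rests on the code.

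The second is timing. One sentence in 8.1 ties HIV status to the earliest look-back contact. The criteria in 7.3.1 and the entry sentence in 8.1 let the diagnosis come later, provided it precedes the risk threshold. Two programmers could follow the same protocol and build different cohorts.

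The study population is people living with HIV. Section 12.1 makes the HIV care arrangement an Aim 1 factor (an HIV doctor together with a primary care practitioner, against the HIV provider alone), and this has no clear meaning for someone without HIV. Section 12.2 draws the Aim 2 matched sample from the Aim 1 population, so an error in case definition carries forward.

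**Working it through.** The plan states no figure on this point, so the check is one of logic.

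**Exclusion 4 against inclusion 2.** Take three recorded facts: HIV code, ART, and whether the ART is prophylaxis (prophylaxis implies ART). Inclusion 2 is met if code AND ART. Exclusion 4 applies if prophylaxis AND no code.

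| HIV code | ART | Prophylaxis | Inclusion 2 met | Exclusion 4 applies | Enters |
|---|---|---|---|---|---|
| no | no | no | no | no | no |
| no | yes | no | no | no | no |
| no | yes | yes | no | yes | no |
| yes | no | no | no | no | no |
| yes | yes | no | yes | no | yes |
| yes | yes | yes | yes | no | yes |

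None of the 6 rows meets inclusion 2 and exclusion 4 together. Crossing with true HIV status gives 6 x 2 = 12 combinations and changes nothing, because neither rule sees true status. The one row that exclusion 4 touches (third) has already failed inclusion 2. The last row holds both a person with HIV and a miscoded HIV-negative prophylaxis user, and nothing in 7.3 separates them.

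**Other readings of exclusion 4.**
- If the absence of a diagnosis is judged when prophylaxis was prescribed, the criterion removes people who took prophylaxis and were diagnosed later. They have HIV and belong in the cohort. The miscoded user with a code already on record still enters.
- The parenthesis opened after pre-exposure prophylaxis is never closed, so the no-diagnosis qualifier might attach to post-exposure use alone. Pre-exposure users would then be removed even with a code, which stops the miscoded ones but also removes people who later acquired HIV. Miscoded post-exposure users still enter.

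**Timing.** Inclusion 3 requires at least one encounter in the 365 days before index, so every patient has at least two contacts and the choice between them can matter. Take three dated contacts:
- A: earliest in the look-back, no HIV code and no ART;
- B: HIV code and ART recorded;
- C: risk threshold first met (index).

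Under the HIV-status sentence in 8.1, status is read at A and the patient is not a case. Under inclusions 2 and 3 and the entry sentence in 8.1, the patient is a case at C. The cohorts differ by the patients first coded or first treated after A and by index.

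**The case against.** The strongest reply is that the governing text is sound. Inclusion 2 needs an HIV-positive diagnosis code and ART, and the site query also selects on HIV diagnosis. Section 8.2 has the study query apply the inclusion and exclusion criteria, and the data characterization query in 8.1.1 will try them out first. A redundant exclusion changes nobody's eligibility.

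Much of this stands, and it limits the point. Four stronger readings are tempting and unsupported:

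- **A reader might infer that HIV-negative prophylaxis users enter because exclusion 4 is redundant, or because of 8.1.** Neither lets anyone in. Entry requires an erroneous HIV code, and the documents do not say how often that occurs.
- **A reader might infer that exclusion 4 can never remove anyone.** That holds on the plain reading. The undefined timing and the unclosed parenthesis leave the two alternatives shown above.
- **A reader might infer that later-coded patients are lost.** Section 8.1 does not say that HIV status is read at the earliest contact and nowhere else. Its promise of time-updated data for other characteristics makes a fixed reading of HIV status plausible, but the result is a conflict between sentences, not a demonstrated loss.
- **A reader might infer that the plan accepts a single code.** The number of codes is simply not stated.

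The reply does not supply a rule that confirms HIV when the only ART is prophylaxis, and it does not remove the disagreement within 8.1.

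**Conclusion.** The point holds as a gap and an inconsistency in the cohort definition. On the plain reading exclusion 4 adds nothing to inclusion 2, and on none of its readings does it fully guard against a miscoded prophylaxis user. The HIV-status sentence in 8.1, read literally, defines a different cohort from 7.3.1 and the 8.1 entry sentence, and the passages must be reconciled.

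No size can be attached to either part. The documents give no frequency of erroneous HIV codes, no share of prophylaxis users among patients with a code plus ART, and no share first coded between the earliest look-back contact and index. They also do not say who provides care to prophylaxis users, so the direction of any distortion in the Aim 1 care factor is unknown. The conclusion rests on taking HIV diagnosis in exclusion 4 to mean the code in inclusion 2, whenever recorded. This is a minor point with a cheap remedy.

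**What to change.** Replace exclusion 4 and the HIV-status sentence in 8.1 by one case definition, stated in 7.3.1 and cited in 8.1:

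1. An HIV code from the inclusion 2 list and an ART prescription, each recorded at any contact on or before index.
2. Where the only ART on record is a prophylaxis regimen of the kind named in exclusion 4, also a second HIV code on a different date or a detectable HIV viral load. The mere presence of a viral load or CD4 result should not count, because a result can exist without showing HIV.

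The query specification should list the prophylaxis regimens in full, since exclusion 4 names the post-exposure one only as an example. The data characterization query can report how many patients rely on step 2, which would give the missing size.

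The cost is query wording, using data that 8.1 already plans to collect, subject to its caveat that the variable list may change with availability. A few true cases on such a regimen with a single code and no detectable viral load would be dropped. Someone with two erroneous codes on different dates would still enter.
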